6.2 Patients randomised to Control Group

Participants randomised to the control group will not receive hysteroscopic resection of their submucous fibroids or endometrial polyps. Participants expecting to receive other fertility treatments e.g. IVF, ovulation induction, IUI, Donor Sperm Insemination, ICSI or medications e.g.

clomid, should resume/commence with this treatment as soon as possible following randomisation. This does not include any research infertility interventions as these are exclusion criteria (exclusion criteria 4).

Women with a strong preference for resection will not be recruited. However, women will have the right to withdraw from their randomised treatment at any time, as is their right (detailed in section 9.2).

7. Randomisation and enrolment

Eligible and consenting participants will be randomised using a centralised web-based randomisation system (SCRAM) hosted by Sheffield Clinical Trials Research Unit (CTRU). This system has user restricted functionalities depending on trial roles. Participants will be allocated on a ratio of 1:1 to either receive hysteroscopic resection of the abnormalities (intervention group) or not (control group). Stratified block randomisation will be used, stratified by 1) recruiting centre and 2) infertility or recurrent miscarriage (both defined in section 5.1). We will not disclose block sizes during the trial. A Trial Statistician will generate the allocation sequence using the SCRAM system. Research staff at recruiting centres will be unable to access the randomisation sequence. A member of the clinical research team will enter participant details onto the system prior to randomisation in order to maintain allocation concealment. Following randomisation, the participant will be informed of their allocation and a record of this will be entered into the patient's medical notes and the next steps in treatment arranged. Some sites may have capacity to facilitate randomisation during the hysteroscopic procedure. In these cases, women randomised to intervention will receive resection during the same procedure. Women randomised to control will not receive resection. Women who are randomised into one of the trials but then go on to develop an abnormality that would render them eligible for the other trial (e.g. randomised into the endometrial polyp trial but then goes on to develop a submucous fibroid) will not be re-randomised and will remain in the trial in which they were originally allocated to, as per ITT (Intention to Treat) principles.

If site staff are unable to access SCRAM, randomisation will be performed centrally by an unblind member of the CTRU team using the same SCRAM system. In the unlikely event SCRAM were to be unavailable, separate back-up randomisation lists will be used. Lists, stratified by site and trial, will be generated by a statistician independent of the HELP study and held in a restricted-access directory on a university drive. Site staff and blinded CTRU staff will not be able to access

the back-up randomisation schedule. Requests for central randomisation can be made via a study-specific email address / telephone number, which will be made available to the site.

7.1 Blinding

The Trial Steering Committee (TSC), the study statisticians and health economists will be blinded to treatment allocation whilst the trial is ongoing. Participants and site staff cannot be blinded due to the nature of the intervention.

7.2 Unblinding

Unblinding of trial statisticians, health economists and the TSC will not take place until the statistical and health economics analysis plans are approved and final data entry and cleaning has taken place (after the final 24 month data collection and again 5 years after consent of the last participant, for the long term follow-up data).

8. Outcomes

8.1 Feasibility outcomes

We have followed the recommendations of Avery et al in setting green/amber/red criteria for both RCTs (34), where green indicates continuation of the trial, any amber indicates that steps should be in place to regain ground and any red indicates the trial is not feasible. Targets will be assessed following 9 months of a 30 month recruitment window. Recruitment targets factor in a staggered site set-up over 7 months. Participant retention will not be assessed as the primary outcome data collection point occurs at 15 months post-randomisation and so inclusion within the stop/go assessment timeframe is not possible.

It is anticipated that the COVID-19 pandemic will impact site waiting times for hysteroscopic resection and these will be monitored during the pilot phase. Timing of primary outcome measurement may require adjustment following this assessment.

If assessment against the criteria indicates that one of the two trials is feasible and the other infeasible, recruitment to the infeasible trial will stop. Only the trial for which recruitment has been feasible will continue. As we anticipate a higher incidence rate in the endometrial polyp trial, a lower than target recruitment rate would therefore still allow completion within the allocated project timescales.

At the end of the pilot phase, the Trial Steering Committee (TSC) will make a recommendation to the NIHR (funder) on whether the feasibility criteria have been met and whether the trial should continue. The TSC may report to the NIHR earlier if the trial meets the feasibility criteria below earlier than expected. Sheffield CTRU will aggregate feasibility of the research and intervention protocols based on the following criteria.

Table 1 Progression criteria for pilot to main trial

Domain	Target at 9m	Green	Amber	Red
Site set-up	30 centres setup and recruited and randomised at least one participant	25 or more centres recruited and randomised at least one participant	15-24 centres recruited and randomised at least one participant	Fewer than 15 centres recruited and randomised at least one participant
Participant recruitment	
Fibroids RCT Average of 0.67 participants recruited per centre per month (approx. 117 in total)
 
Polyps RCT Average of 1.3 participants recruited per centre per month (approx. 227 in total)
	
Fibroids RCT Minimum 80% of target (per centre per month)
 
Polyps RCT Minimum 40% of target (per centre per month)
	
Fibroids RCT 60-80% of target (per centre per month)
 
Polyps RCT 30-40% of target (per centre per month)
	
Fibroids RCT Below 60% of target (per centre per month)
 
Polyps RCT Below 30% of target (per centre per month)

Number of women randomised to intervention (resection) and receiving resection treatment within three months of randomisation*	100% of intervention participants received intervention before 3 months post randomisation	80% of intervention participants received intervention before 3 months post randomisation. No change to timing of primary endpoint e.g. LBR at 15 months post randomisation.	Less than 80% of intervention participants received intervention before 3 months post randomisation. Consider a change to the primary endpoint point e.g. to 18 or 21 or 24 months post-randomisation	Not applicable.

Withdrawal from control treatment (receiving resection) before 6 months post randomisation	0% of control participants received intervention before 6 months post randomisation	Fewer than 10% of control participants received intervention before 6 months post randomisation	Between 10-50% of control participants received intervention before 6 months post randomisation	Greater than 50% of control participants received intervention before 6 months post randomisation
--------------------------------------------------------------------------------------------	-------------------------------------------------------------------------------------	-------------------------------------------------------------------------------------------------	-------------------------------------------------------------------------------------------------	---------------------------------------------------------------------------------------------------

Note: Fulfilment of the 'green' criteria indicates continuation of the trial, fulfilment of the amber criteria indicates that steps should be in place to regain ground, fulfilment of the red criteria indicates the trial is not feasible.

* The primary endpoint is the LBR at 15-months post-randomisation; if in the pilot phase we find that fewer than 80% of the participants randomised to the intervention are receiving the treatment with 3-months of randomisation then we will consult with the TSC and DMEC about increasing the timing of the primary outcome to 18, 21 or 24 months post-randomisation. The LBR at 24 months post randomisation is already a secondary outcome.

Numbers of incorrect diagnosis/absence of abnormalities identified at surgery will be monitored during the internal pilot phase. Participant screening methods (section 5.3.1) may be modified if the proportion of participants identified as misdiagnosed is unacceptably high.

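### Table 1 reads 6-month control crossover and 3-month resection uptake as plain percentages at month 9, when most women lack that follow-up, so crossover looks too low and uptake looks too poor

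*Protocol*

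**What the plan says.** Section 8.1 fixes the time of the reading: "Targets will be assessed following 9 months of a 30 month recruitment window". It adds "Recruitment targets factor in a staggered site set-up over 7 months", and the site target is "30 centres setup and recruited and randomised at least one participant".

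Table 1 then sets two criteria that depend on elapsed time from randomisation:

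- **Control crossover by 6 months.** Green is below 10%; amber is "Between 10-50% of control participants received intervention before 6 months post randomisation"; red is "Greater than 50% of control participants received intervention before 6 months post randomisation".
- **Resection by 3 months in the intervention arm.** Green is 80%; below 80% is amber and leads to considering a primary endpoint at 18, 21 or 24 months. There is no red level.

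The recruitment targets at month 9 are, for fibroids, "Average of 0.67 participants recruited per centre per month (approx. 117 in total", and for polyps, "Average of 1.3 participants recruited per centre per month (approx. 227 in total". Section 7 states the allocation: "Participants will be allocated on a ratio of 1:1 to either receive hysteroscopic resection", so controls are half of those randomised.

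Section 8.1 treats any red as showing the trial to be infeasible, and each RCT is judged on its own. It leaves retention out because the 15-month outcome cannot be seen by month 9. It makes no such allowance for the 6-month or 3-month windows. Table 1 expresses both criteria as percentages of control or intervention participants. It neither restricts them to women who have completed the window nor uses a time-to-event estimate.

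**The concern.** A woman randomised in month 8 has been at risk of crossover for one month when the criterion is read. Counted in the denominator, she is a non-crossover before her six months are up. Because accrual is weighted towards the later months of the pilot, most women are in this position. The same applies to intervention women still waiting for their procedure.

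Both criteria protect the primary comparison. Section 8.2 argues that crossover will barely disturb the 15-month live birth rate and relies on Table 1 to check this. Section 11.2 says that substantial early resection of controls, or late resection in the intervention arm, could leave the 15-month comparison without a valid estimate of the effect of resection. A reading that is biased by design can therefore clear a crossover problem that exists, or signal a waiting-time problem that does not.

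**Working it through.** **1. Reproduce the plan's recruitment figures.** Centre-months = target / rate: 117/0.67 = 174.6 and 227/1.3 = 174.6. The protocol does not give the shape of site opening. A whole-number, roughly linear ramp to 30 centres over 7 months, then two months at 30 (4, 8, 12, 16, 20, 25, 30, 30, 30), sums to 175 centre-months. That gives 175 × 0.67 = 117.3 and 175 × 1.3 = 227.5, matching both targets. Monthly steps of 30/7 (180 centre-months) and a continuous ramp (165) serve as a range.

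**2. Women with complete follow-up at month 9.**

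- 6 months (recruited in months 1-3): (4 + 8 + 12)/175 = 24/175 = 13.7%; range 11.7-14.3%.
- Fully followed controls: 24 × 0.67/2 = 8.0 fibroid (range 6.5-8.6) and 24 × 1.3/2 = 15.6 polyp (range 12.5-16.7).
- 3 months (recruited in months 1-6): 85/175 = 48.6%; range 47-50%.
- If the two-week data window in section 9 is also allowed for, the 6-month share falls to (4 + 8 + 6)/175 = 18/175, about 10%.

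**3. Crossover with all controls in the denominator.** The expected reading is the average, over recruitment times *t*, of F(min(6, 9 − *t*)), where F is the cumulative crossover distribution. The protocol does not give its shape, so four are shown (175 centre-month ramp):

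| Crossover timing | True 60% reads | True 10% reads | True rate needed to read 50% |
|---|---|---|---|
| Constant hazard (−ln 0.4/6 = 0.153 per month at 60%) | 35% | 5.3% | just under 80% |
| Even over months 0-6 (multiplier 0.519) | 31% | 5.2% | 0.50/0.519 = 96% |
| Even over months 3-6 (multiplier 0.294) | 18% | 2.9% | not reachable |
| Even over months 0-3 (multiplier 0.743) | 45% | 7.4% | 0.50/0.743 = 67% |

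Section 8.2 expects crossover to come late, so the last row is the least likely.

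**4. Uptake with all intervention women in the denominator.** The reading is the average of F(min(3, 9 − *t*)). With a true 90% resected within 3 months and a constant hazard (−ln 0.1/3 = 0.768 per month), it is 75%. With even timing over 0-3 months it is 0.90 × 0.743 = 67%. Both fall below the 80% green limit.

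**5. Fully followed controls only.** This is unbiased but thin. The exact 95% CI is 16-84% for 4 of 8 and 25-75% for 8 of 16. With 8 controls, red needs 5 or more: probability 0.59 at a true 60% and 0.17 at a true 40%.

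**6. Kaplan-Meier at month 9.** Simulated with the same ramp, constant hazard, and 58 fibroid or 113 polyp controls (half of 117 and of 227). A true 60% averages 60%, with SD about 12 points (fibroid) and 8 points (polyp). The estimate exceeds 50% in about 80% and just under 90% of runs. A true 30% exceeds 50% in about 3-4% (fibroid) and under 1% (polyp).

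**The case against.** The strongest reply is that month 9 is neither mechanical nor final. Amber still calls for corrective steps, so a true 60% that reads 35% is flagged. Red leads to a steering committee recommendation to the funder. The DMEC receives monthly reports and may advise stopping or modifying the trial, and control resections are counted as a secondary outcome. The analysis plans adjustments for non-compliance and treatment switching. The choice of estimator is often left to an analysis plan.

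Much of this stands and limits the severity. It does not remove the point: Table 1 itself fixes the quantity, the cut-offs and the date, and applied as written to all participants the quantity misclassifies.

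Four stronger readings are tempting, and the documents do not support them:

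- *A red crossover rate would always pass as amber.* Very high or very early crossover would still read red (step 3), and the protocol states neither the crossover timing nor, in so many words, the denominator.
- *The decision rests on 6-9 controls.* That is the fibroid RCT only; the polyp RCT has about 13-17 fully followed controls at target.
- *Both criteria flatter the trial.* Uptake errs the opposite way. It has no red level, and amber leads only to consultation. Women randomised during hysteroscopy are resected at once, which would shrink that bias by an amount the protocol does not allow one to estimate.
- *The decision must wait until month 15.* Six further months at 30 centres add 6 × 30 × 0.67 = 121 fibroid and 6 × 30 × 1.3 = 234 polyp women, making 238/560 (42%) and 461/560 (82%). A stop/go decision with 82% of the polyp trial recruited would defeat the purpose of an internal pilot.

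**Conclusion.** The point holds in this form. At month 9, and at target recruitment, about one woman in seven has the 6-month follow-up and about half have the 3-month follow-up that Table 1 presupposes. With all randomised women counted, a true crossover of 60% reads about 18-35% (45% if every crossover falls in the first 3 months), and a true 10% reads about 3-5%. A true uptake of 90% reads about 75%. So the crossover check errs towards continuing, and the uptake check errs towards reopening the primary endpoint.

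The size rests on roughly linear site opening, a constant recruitment rate per open centre and the crossover and uptake timings shown; the protocol states none of these. The direction of both biases does not depend on them. The amendment should be made, but it is a matter of definition and does not put the design of either RCT in doubt.

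**What to change.** In Table 1, define both timing criteria as Kaplan-Meier estimates from randomisation: resection by 6 months in controls and by 3 months in the intervention arm. Censor at the month-9 data cut, report by RCT with 95% confidence intervals, and apply the existing red/amber/green limits to those estimates. Report the crossover estimate again to the TSC and DMEC as follow-up matures, without deferring the month-9 decision.

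The cost is a change of wording in Table 1 and slightly more analysis. It also needs resection status and date up to the cut for women who have not reached their 6-month contact. The month-9 estimate stays imprecise (SD about 12 points fibroid and 8 points polyp at a true 60%), so the committees should read the interval as well as the colour.

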8.2 Primary outcome

1. Live birth rate (LBR) defined by the number of live births after 24 weeks gestation within the 15-month post-randomisation follow-up period relative to the number of women randomised. Multiple live births (e.g. twins) will contribute one event to the numerator in the calculation of the live birth rate. This will be assessed by either review of the participant's medical notes (if the patient is still receiving treatment from the centre/hospital in which she was randomised), or, if the patient has commenced treatment elsewhere or has been discharged, telephone contact with the participant will be performed by the Clinician/Research Nurse/Midwife/Associate PI/Dr.

We have chosen 15 months post-randomisation as the cut-off for live births as this is potentially sufficient time for women in the intervention arm to have resection, conceive and give birth. It is possible that some women in the control arm may decide to withdraw

from their allocated treatment and undergo resection. However, in such cases we anticipate women would be unlikely to receive resection within 6 months of randomisation. This means that the estimated live birth rate up to 15 months follow-up in the randomised groups is unlikely to be confounded by the effect of women in the control arm undergoing resection. However, given the uncertainty around these estimates, the timing of the primary outcome will be reviewed as part of the progression criteria from pilot to main trial (see Table 1).

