- Time to live birth, time to pregnancy, pregnancy rate, miscarriage, premature labour, multiple birth, still birth, ectopic pregnancy, adverse events, details of fertility treatments received, COVID-19 vaccination status and health resource use.
- Adverse event information

The health resource use questionnaire will be sent directly to the patient from the CTRU via post or online.

24 month post-randomisation (and up to LPLV)

Members of site staff will be asked to record the following from patients' medical notes and / or telephone contact with the participant;

- Adverse event information
- Time to live birth, time to pregnancy, pregnancy rate, miscarriage, premature labour, multiple birth, still birth, ectopic pregnancy, adverse events, details of fertility treatments received and COVID-19 vaccination status.

The health resource use questionnaire will be sent directly to the patients from the CTRU via post or online.

Table 2 – Data collection time points

	Eligibility assessment	Baseline/ randomisation	Directly post-hysteroscopy #	6 months*	15 months*	24 months*	Post 24 months to Last Patient Last Visit (LPLV)	Long term (minimum 5 years post randomisation)
Demographics – age, fertility markers, previous fertility treatment received, type of infertility (infertility/recurrent miscarriage), BMI, smoking status.	MN	IP/MN						
Details of uterine abnormalities (size, grade)	MN	MN	MN					
Patient satisfaction			Q#					
Live birth rate (primary outcome)					T/MN (primary outcome)	T/MN		MN/NHSD
Time to live birth					T/MN	T/MN	MN	
Time to pregnancy				MN	T/MN	T/MN	MN	MN/NHSD
Pregnancy rate				MN	T/MN	T/MN	MN	MN/NHSD
Miscarriage				MN	T/MN	T/MN	MN	MN/NHSD
Premature labour					T/MN	T/MN	MN	

HELP Fertility?

Multiple birth					T/MN	T/MN	MN	
Still birth					T/MN	T/MN	MN	MN/NHSD
Ectopic pregnancy				T/MN	T/MN	T/MN	MN	
Adverse events; obstetric, gynaecological or procedure related complications			IP/T/MN	T and MN	T and MN	T and MN	MN	
Obstetric outcomes				T/MN	T/MN	T/MN	MN	
Details of hysteroscopy received (intervention arm only)			MN	MN	MN	T/MN	MN	MN/NHSD
Details of fertility treatments received (clomid, IVF, IUI etc.)				MN	MN	MN	MN	MN/NHSD
Health resource use,		Q/MN		Q/MN	Q/MN	Q/MN		
Patient cost questionnaire			Q					
Time post surgery abstaining from sexual intercourse [#]				T/Q				
COVID-19 vaccination status (1 st , 2 nd , booster, approximate date and type of vaccine)		T/Q		T/Q	T/Q	T/Q	T/Q	

HELP Fertility?

* Time points measured from randomisation

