Intervention arm only

IP = in person, MN = medical notes

T = telephone contact with patient

Q = questionnaire, administered via post/email/online

NHSD = NHS Digital

Long term follow-up

Long term follow-up data will be collected 5 years after the final patient was recruited in one of two ways;

- 1) The clinic / hospital in which participants were randomised will be asked to check the medical records of those who gave consent for long term data collection. If the patient commenced treatment elsewhere, telephone or postal contact may be made with the participant by a member of the clinical research team.
- 2) An application will be made to NHS Digital requesting access to data from those who have agreed to this on the consent form. The names, date of birth and NHS number will be sent to NHS Digital for data linkage. Accessing data from NHS Digital is likely to result in increased data completeness compared to following up participants manually over this time frame, due to the likelihood of participants changing address and the risk of a low response rate (if followed up via questionnaire) or being discharged from the recruiting centre and receiving treatment/maternity care at another hospital (if followed up using local medical records).

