10.2 Recording and reporting

AEs and SAEs are defined as an event that occurs after the patient has provided written informed consent for trial entry and up to completion of the 24 month follow-up by the last participant recruited (LPLV).

Hysteroscopic resection of submucous fibroids and endometrial polyps is a routine procedure for which the side effects are understood. Therefore, only those AEs which are deemed serious or of particular relevance to the procedure will be recorded / reported in this trial. These are listed as 'expected AEs' in Table 4.

Adverse Events

Participants will be asked for any details of adverse events, at four time points up to the participants' final study related follow-up event; post procedure (if randomised to receive hysteroscopic resection of submucous fibroids or endometrial polyps), then at 6, 15 and 24 months post randomisation. AEs or SAEs may also be identified by the Research Nurse/Associate PI/Dr, or any other individual, at any point during the study, up to last patient last visit.

When an event is identified the process for recording and reporting outlined in Figure 5 will be followed. The local PI (or other suitably trained member of research staff, if the task is delegated to them) should be notified immediately and assess the event for classification as an SAE (see definition in section 10.1).

AEs confirmed as NOT serious will be checked against the list of expected AEs (Table 4).

Expected AEs

AEs which are expected will be recorded by site staff in the participant CRF.

Unexpected AEs

AEs which are not expected will not be recorded on the basis that hysteroscopic resection of submucous fibroids and endometrial polyps is a routine procedure, for which the side effects are understood. We do not anticipate any AEs, which are of relevance to the intervention, other than those listed in Table 4, unless the site PI considers the events to be significant.

Sites are asked to enter all available information onto the study database as soon as possible after the site becomes aware of the event.

Table 4 - Expected Adverse Events

Gynaecological / obstetric related	Procedure related (immediate)	Procedure related (delayed)

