11.1 Sample size

The primary outcome for both trials will be live birth rate (LBR) defined by the number of live births after 24 weeks gestation within the 15-month post-randomisation follow-up period relative to the number of women randomised.

Our review of the research literature including a Cochrane review of hysteroscopic removal of submucous fibroids and endometrial polyps (6) has found no reported estimates of the LBR in our proposed target populations. Although, two previously conducted RCTs included in the Cochrane review roughly indicate a doubling of pregnancy rates. The first quoted a clinical pregnancy rate (at 6-7 weeks) of approximately 214/1000 (21%) over 12 months in a sample of 42 women with fibroids (submucosal and mixed submucosal intramural) without surgery and a miscarriage rate (between 7 and 12 weeks) in those without surgery of approximately 556/1000 (56%) (35). Applying the miscarriage rate to the pregnancy rate (i.e. $0.21 * 0.56$) would give a LBR of approximately 10% over 12 months in the control arm (no resection). The second, in women with endometrial polyps undergoing IVF, detected an increase of pregnancy rates from 28% to 63%, with no miscarriage rate reported (36). We therefore estimate a usual care LBR of 10% within 15 months in the populations of women proposed for inclusion in this study, both for the submucous fibroid and endometrial polyp RCTs.

Assuming a 10% LBR in the no hysteroscopic removal (control) group and that an absolute increase of 10%, to a 20% LBR (a relative risk of 2.00) in the hysteroscopic removal (intervention) group is of clinical and practical importance. Then to have a 90% power of detecting this difference or more, in LBR rates between the groups, as statistically significant at the 5% two-sided level, will require 266 women per group (532 in total). Adjusting for a predicted attrition rate of 5% (due to potential difficulties of follow-up for patients who have been referred from other NHS Trusts) we will require 560 participants to be randomised.

A similar sample size will be required for RCT2 (polyp population) i.e. 560 participants, so a total of 1120 participants are required for RCT1 and RCT2 combined.

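### The 15-month live birth outcome may rest on the randomising unit's notes alone for women still treated there, although a contact about adverse events is planned for the same visit

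*Protocol*

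**What the plan says.** Section 8.2 makes the source of the primary outcome an either/or. It is "medical notes (if the patient is still receiving treatment from the centre/hospital in which she was randomised"), or a telephone call if she has been discharged or has started treatment elsewhere.

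Section 9.1, in the 15-month text, is looser: notes and/or telephone, with no condition attached. Adverse events sit in the same and/or list at 15 months, and again at 24 months.

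Table 2 gives the live birth source at 15 months as "T/MN (primary outcome"), that is, telephone or notes. Pregnancy at 6 months is marked notes only, although the 6-month text in 9.1 allows notes and/or telephone. By contrast, the Table 2 row "Adverse events; obstetric, gynaecological or procedure related complications" is marked T and MN at 6, 15 and 24 months, with T defined as telephone contact with the patient.

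Section 10.2 agrees with that row: "Participants will be asked for any details of adverse events, at four time points", three of which are 6, 15 and 24 months after randomisation.

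Section 11.2 uses all women randomised as the denominator, counts an unknown outcome as no live birth, and plans best-case and multiple-imputation sensitivity analyses for missing birth outcomes.

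**The concern.** The primary endpoint has a weaker source rule than adverse events at the same visit. A woman can still be a patient of a fertility or gynaecology unit and deliver at a different hospital. The switch from notes to telephone also works only if the unit knows that she has moved, and the notes may not show it.

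The protocol does not separate notes that show no birth from notes that are silent. If a silent record is entered as a negative outcome, it is no longer missing. The best-case and multiple-imputation analyses act only on outcomes recorded as unknown, so they would leave that record untouched.

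At stake is some dilution of the difference if births are missed equally in both arms, and bias if they are not. Being still under treatment at the centre at 15 months is a state reached after randomisation in an open trial, so the share of women classified from notes could differ by arm.

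**Working it through.** **Inputs (Protocol 11.1):** "Assuming a 10% LBR in the no hysteroscopic removal (control) group", 20% in the intervention group, "90% power of detecting this difference or more", "statistically significant at the 5% two-sided level", 266 per group, 5% attrition, 560 per trial. Allocation is 1:1 (section 7), so 280 per group.

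**1. Reproduce the plan's figure.** Pooled-variance formula, no continuity correction:

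n = [1.960·√(2·p̄(1−p̄)) + 1.282·√(p1(1−p1)+p2(1−p2))]² / (p2−p1)²

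With p1 = 0.10, p2 = 0.20, p̄ = 0.15: √(2·0.15·0.85) = 0.505 and √(0.09+0.16) = 0.500, so n = 265.9, rounded up to 266 per group. Then 532/0.95 = 560. Both figures reproduce.

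**2. Choose the n for the effect of missed births.** Unknown outcomes count as no live birth and everyone randomised is in the denominator, so the analysed number is 280 per group, not 266:

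Power = Φ{[|p2−p1|·√n − 1.960·√(2·p̄(1−p̄))] / √(p1(1−p1)+p2(1−p2))}

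This gives 90.0% at 266 and 91.4% at 280.

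**3. Equal misses.** If a share m of births is missed in both arms, the observed rates are 0.10(1−m) and 0.20(1−m). The values of m are assumptions; the documents give none.

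| m | Observed rates | Difference | Power at 280 per group |
|---|---|---|---|
| 0% | 10.0% v 20.0% | 10.0 points | 91.4% |
| 5% | 9.5% v 19.0% | 9.5 points | 89.7% |
| 10% | 9.0% v 18.0% | 9.0 points | 87.8% |
| 20% | 8.0% v 16.0% | 8.0 points | 83.1% |
| 30% | 7.0% v 14.0% | 7.0 points | 77.2% |

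Here m is a share of all births in the arm. Only births in the residual group can be missed by this route, so m is the share of births in women classified from notes alone, multiplied by the share of those births absent from the notes. The 20% and 30% rows would need both factors to be large. In counts, 280 per group at the design rates means 28 and 56 births; missing 10% loses 2.8 and 5.6 of them.

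**4. Unequal misses (also assumed).**
- 10% missed in the intervention arm only: 0.20·0.90 − 0.10 = 8.0 points, power 78.0%.
- 10% missed in the control arm only: 0.20 − 0.10·0.90 = 11.0 points.
- 8% missed in the intervention arm and 3% in controls: 0.20·0.92 − 0.10·0.97 = 8.7 points, power 84.4%. With no true effect (10% in both arms): 0.092 − 0.097 = −0.5 points, two-sided rejection rate about 5.5%.
- No true effect and 20% missed in one arm only: rejection rate about 13%.

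**5. Set the passages side by side.**

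| Item at 15 months | 8.2 | 9.1 text | Table 2 | 10.2 |
|---|---|---|---|---|
| Live birth | notes, or telephone if discharged or elsewhere | notes and/or telephone | T/MN | – |
| Adverse events | – | notes and/or telephone | T and MN | woman is asked |

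Two sources require contact about adverse events; one does not. None requires every woman to be asked about birth.

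**The case against.** The case against has real force, and much of it stands.

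- **Section 8.2 already calls the women most at risk.** Those discharged or treated elsewhere are the likeliest to deliver elsewhere, and they get a telephone call. A reader might infer that the protocol itself concedes that local notes miss births at 15 months, because it refers to "receiving treatment/maternity care at another hospital (if followed up using local medical records"). It does not go that far. The sentence concerns long-term follow-up and joins this risk to discharge from the recruiting centre, which is the group that 8.2 sends to a call. The mechanism carries over only to the residual group.
- **An adverse-event call would often reveal a birth.** Table 4 includes post-partum haemorrhage and manual removal of the placenta. A reader might conclude that every woman is certainly telephoned at 15 months. Table 2 and 10.2 point that way, but the 9.1 text lists adverse events under and/or, so the contact is planned and not fully secured.
- **Later data may recover missed births.** Time to live birth is collected again at 24 months and up to the last participant's last visit, and unblinding waits for the final 24-month data and cleaning. A resource-use questionnaire also goes to every woman at 15 and 24 months, though each covers only the preceding 3 months.
- **The coding of a silent record is inferred.** No text says that it becomes an observed negative. The protocol leaves that open and does not prevent it. An unknown code would not change the primary analysis, which already counts unknown as no live birth; it would change only the sensitivity analyses.
- **Differential misses have no source.** More contact with the centre could equally mean fuller notes. The 8% v 3% split, and its direction, are illustrative.

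What remains is a weak and inconsistent source rule for the primary endpoint, beside a stronger rule for adverse events at the same visit.

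**Conclusion.** The point holds in limited form. The protocol permits notes-only ascertainment of the primary outcome for women still treated at the randomising centre, and 8.2, 9.1 and Table 2 do not agree on when the woman must be asked. The exposed group is women on the unit's books who deliver at another hospital, or whose move the unit has not learned of.

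If misses are few and equal between arms, the cost is small: 91.4% power falls to 89.7% or 87.8% for 5% or 10% of births missed, and the 10-point difference reads 9.5 or 9.0. Unequal misses would bias the estimate in either direction, and a larger sample would not repair that. The documents show neither the miss rate nor any imbalance, so they do not support a claim that the primary result will be biased or that the sample size is wrong; 266 per group and 560 per trial stand. The figures rest on the design rates, all 280 randomised per group being analysed, and silent notes being entered as no live birth.

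The change is worth making because it is cheap and protects the primary endpoint, not because a large bias has been demonstrated.

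**What to change.** 1. Reconcile 8.2, 9.1 and Table 2 so that adverse events and pregnancy (6, 15 and 24 months) and live birth (15 and 24 months) are all sourced from telephone and notes.
2. On the contact already scheduled, ask women in both arms about pregnancy and birth, with dates, and use the notes to confirm. Rely on notes alone only when the woman cannot be reached.
3. Record the source used for each outcome, so that the share classified from notes can be compared between arms.
4. When the woman is not reached and the notes are silent, code the outcome as unknown. The primary analysis rule is unchanged, but the best-case and multiple-imputation analyses in 11.2 then cover these women.

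**Cost:** a few more questions on the telephone proforma, plus protocol and CRF wording. There is no extra visit and no change to the sample size. Some more outcomes will be recorded as unknown, which will widen the gap between the default and best-case results; that gap would then show real uncertainty that is now hidden.
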